15.1. Ethics committee and regulatory authorities

The CIP and/or other relevant documents are submitted to the appropriate EC(s) and regulatory authorities. This clinical investigation will not begin until the required approval from the EC and regulatory authorities have been obtained. Any amendment to the protocol will be submitted to the same EC(s) and regulatory authority.

Sponsor will notify the relevant regulatory authority and EC(s) concerned of the end of the clinical investigation.

15.2. Data protection

As part of the investigation Coloplast A/S, [REDACTED] (“Coloplast”) will collect and process the personal information the subject provides for the investigation (“subject personal data”). This includes identification and contact information (which may be anonymised depending on the nature of the investigation) as well as information about product usage experience and your health. Coloplast will only process the subject's personal data:

1. To conduct the investigation and carry out related research based on subject consent (primary use), cf. article 9(2)(a) of the EU General Data Protection Regulation (GDPR),
2. To comply with applicable legal obligations to e.g., ensure reliability and safety, cf. article 6(1)(c) in conjunction with article 9(1)(i) of GDPR, and
3. If separate consent is given for secondary use of subject personal data, cf. article 9(2)(a) of GDPR –carry out research outside the clinical protocol to improve Coloplast's products and services, and for use in education.

Part of Coloplast's processing is carried out on third-party platforms (clinical trial databases) and certain third parties are assisting Coloplast in the processing (e.g., the investigator). Such cases will imply a transfer of your personal data to the third parties, but solely for the specified purposes and with the third parties acting on instruction from Coloplast. Data may be collected and processed across the Coloplast network, which may entail processing of personal data outside the European Economic Area. In such cases, an adequate level of protection will be ensured by the third parties being subject to the standard contractual clauses on data protection adopted by the EU or to an EU-approved certification mechanism on data protection. For further information about this please the subject can always consult Coloplast's data protection officer (details below).

Subject personal data will be kept as long as required under applicable laws and regulations. The EU Medical Device Regulation obligates Coloplast to keep the data for a period of at least ten years after the investigation is completed, or, in the event that the device is subsequently placed on the market, at least ten years after the last device has been placed on the market. Subject personal data will be deleted at the end of the mandatory retention period.

[figure not shown]
If the subject has questions or queries regarding Coloplast's handling of personal information, the subject can always contact Coloplast's Data Protection Officer at [REDACTED] Complaints related to Coloplast's handling of subject personal information may similarly be sent to the Data Protection Officer, and the subject are also entitled to file a complaint with the relevant supervisory authority, which in the case of Denmark is the Danish Data Protection Agency (www.datatilsynet.dk).

The subject can write to [REDACTED] at any time to request:

1. Access to personal data
1. Correction of errors in personal data or to erase personal data
1. Limit what can be done with personal data
1. To receive personal data in machine-readable format (data portability).
1. Withdrawal of consents the subject has given Coloplast to process personal data

15.3. Indemnity

All subjects are fully covered by Coloplast A/S insurance throughout the investigation:

15.4. Financial conditions

Coloplast A/S will compensate all investigators involved in the clinical investigation for their time and resources spent on the investigation. All financial agreements with the investigation sites involved in the clinical investigation will be specified in a sponsor investigator agreement.

The expenses include the salary to the Principal Investigator, the cost of external clinical support, study supplies, eCRF, Investigator and site personnel training and patient expenses including travel expenses.

The Principal Investigator and site personnel have no financial interests in the investigation.

The total budget for the investigation is [REDACTED] covering 50 subjects.

16. Informed consent process

Written informed consent is obtained from all subjects participating in the investigation after thorough written and verbal information. The information is given by the investigator or his/her representative in the subjects' native non-technical language. Each subject will be fully informed about the aim of the investigation, procedures, potential risks, or inconveniences and/or expected benefits, all anticipated adverse device effects and then have a minimum of 24h before deciding on participation. The subjects will be informed that their participation is voluntary and that they may leave the investigation at any time, without this having any influence on their further treatment.

The informed consent signature form includes personally dated signatures of the subject and the PI or his/her representative responsible for conducting the informed consent process. A copy will be provided to the subject.

If new information is to be given during the investigation, sponsor will inform the investigators, and the new information is given to the subjects by the investigator. If new information becomes available that can significantly affect a subject's future health and medical care that information will be provided to the subject in written form. The Clinical Manager is responsible for writing the information and providing it to investigators that will further provide it to the subjects. If applicable, all affected subjects shall be asked to confirm their continuing informed consent in writing.

17. Subject compensation

17.1. Compensation in case of injury

Product liability and No-Fault Clinical Investigation Insurance covering the duration of the clinical investigation are in place, to enable compensation in the event of an injury to a participating subject. See section 15.3

17.2. Compensation for participating in the clinical investigation

Subjects are compensated for any transportation costs.

Reimbursement of transportation expenses are not taxable per local legislation. Transport expenses will be paid in appropriate portions that justify the administration throughout the investigation period.

Subjects will be compensated with a voucher per test visit, paid by Coloplast A/S with the value as described below:

Visits	Subjects
Visit 1 (V1)	[REDACTED]
Visit 2 (V2)	[REDACTED]
Visit 3 (V3)	[REDACTED]

18. Adverse events, adverse device effects and device deficiencies

18.1. Adverse events

An adverse event is any untoward medical occurrence, unintended disease or injury, or untoward clinical signs (including abnormal laboratory findings) in subjects, whether or not related to the investigational medical device(s), or the procedures involved. The adverse event shall be marked with the intensity mild, moderate, or severe. This could include events such as headache or dizziness.

18.2. Adverse device effect

An adverse event, which is related to the use of the investigational medical device, is an adverse device effect, and should be marked as unlikely related, possible related, probably related or with causal relationship on the adverse event form.

The definition of an adverse device effect includes any event resulting from insufficiencies or inadequacies in the instruction for use, or any malfunction of the medical device, as well as any event resulting from use error or from intentional misuse of the device.

The anticipated adverse device effects in this investigation are considered equal to the use of other wound care products on the marked (with silver). Risks associated with the use of wound care products are skin irritation/inflammation, allergic skin reaction, maceration, pain, hyper-granulation, and blistering.

Table 4 lists anticipated adverse device effects that may occur, and their likely incidence rates based on adverse event reported in clinical studies on other silver containing products (2-7)

Table 4. Anticipated adverse device effects and their likely incidence rates

ANTICIPATED ADE	INCIDENCE RATE
Skin irritation/inflammation	10 %
Allergic skin reaction	1%
Maceration	10%
Pain	10%
Hyper-granulation	5%
Blistering	2%

18.3. Device deficiency

A device deficiency is the inadequacy of the investigational medical device or comparator with respect to its identity, quality, durability, reliability, safety, or performance. This includes malfunctions, use errors and inadequacy in the information supplied by the manufacturer including labelling.

18.4. Serious adverse events (SAE)

A serious adverse event is an adverse event that:

- Led to death,

- Led to a serious deterioration in the health of the subject, users or other persons as defined by one or more of the following:
 - 1) a life-threatening illness or injury, or
 - 2) a permanent impairment of a body structure or a body function including chronic diseases, or
 - 3) in-patient or prolonged hospitalization, or
 - 4) medical or surgical intervention to prevent life-threatening illness or injury or permanent impairment to a body structure or a body function.
- Led to foetal distress, foetal death or a congenital abnormality or birth defect including physical or mental impairment.

This includes device deficiencies that might have led to a serious adverse event if:

- 1) Suitable action had not been taken, or
- 2) Intervention had not been made, or
- 3) Circumstances had been less fortunate.

These are handled under the serious adverse event reporting.

Planned hospitalization for a pre-existing condition, or a procedure required by the CIP, without serious deterioration in health, is not considered a serious adverse event.

18.4.1. Serious adverse device effect (SADE)

A serious adverse device effect is an adverse device effect that has resulted in any of the consequences characteristic of a serious adverse event.

18.4.2. Anticipated serious adverse device effect (ASADE)

Anticipated serious adverse device effect is any event that by its nature, incidence, severity, or outcome has been previously identified in the risk analysis report.

18.4.3. Unanticipated serious adverse device effect (USADE)

An unanticipated serious adverse device effect is a serious adverse device effect which by its nature, incidence, severity or outcome has not been identified in the current version of the risk analysis report.

18.5. Medical care of subjects

Principal investigator shall ensure that adequate medical care is provided to a subject experiencing an adverse event during and after participation in the clinical investigation. All ongoing ADEs, SAEs, SADEs and DDs, that could have led to a SAE at subject termination, will be followed according to the Risk Benefit analysis (see 8.2) and will be followed until a resolution is addressed for a period of 2 months after subject termination. An ongoing adverse event at subject termination visit is documented as the current status for the adverse event and will not be followed up.

The subjects shall be informed of any new significant findings occurring during the clinical investigation, including the need for additional medical care that can be required, and of the nature and possible cause of any adverse events experienced

Principal Investigator or delegate shall provide the subject with the necessary instructions on proper use, handling, storage and return of the test products, when it is used or operated by the subject.

18.6. Reporting and timelines

All adverse events and device deficiencies will be reported in the eCRF. If, for some reason, the system is off-line, investigators (or designee) are required to report the event to: [REDACTED]

18.7. Investigator's reporting responsibilities

- PI at each site must assess all (S)AE's that occur at his/her site.
- All serious adverse events and serious adverse device effects must be reported to sponsor within 24 hours of the site becoming aware of the event.
- A device deficiency that could have led to a serious adverse event but did not because suitable action was taken, intervention had been made or because of fortunate circumstances should be reported to sponsor within 24 hours of the site becoming aware of the event.
- New findings and/or updates in relation to already reported serious events should also be reported to sponsor within 24 hours of the site becoming aware of the event.
- Device deficiencies and all adverse device effects must be reported to the sponsor within 24 hours of becoming aware of the event.

When reporting the SAE, the relationship to the test material shall be described whether the event is considered

- **Not related**, the event has no temporal relationship with the use of the test material or the procedures.
- **Unlikely related**, the relationship with the use of the test material seems not relevant and/or the event can be reasonably explained by another cause, but additional information may be obtained.
- **Possibly related**, the relationship with the use of the test material is weak but cannot be ruled out completely. Alternative causes are also possible (e.g., an underlying or concurrent illness/ clinical condition or/and an effect of another device, drug or treatment). Cases where relatedness cannot be assessed, or no information has been obtained should also be classified as possible.
- **Probably related**, the relationship with the use of the test material seems relevant and/or the event cannot reasonably be explained by another cause, but additional information may be obtained.
- **Definitely related/Causal relationship**, the event has a temporal relationship with the test material use/application or procedures.

and the intensity of the event should be considered, as such:

- **Mild**, the intensity of the event is mild with no further action or intervention
- **Moderate**, the intensity of the event will lead to an action or intervention to solve the event
- **Severe**, the intensity of the event will lead to follow up on the action or intervention, as the effect of the action or intervention may not decrease the symptoms.

All above events must be reported by use of the relevant adverse event/serious adverse event/device deficiency form.

Please report to: [REDACTED] and [REDACTED] In cases where accessing e-mail is not possible, please call [REDACTED]

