Several clinical investigations on silver containing gelling fibers have been published mainly in the chronic wound indication venous leg ulcers and the acute wound indication burns. The wound indication burns have therefore been chosen for the clinical study providing clinical data on an acute wound indication. The data obtained in the clinical investigation will in the Clinical Evaluation Report be evaluated and compared to the data available on similar devices to ensure the performance and safety profile for Biatain Fiber Ag is similar to other antimicrobial gelling fibers.

3. Objective of the clinical investigation

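### The relatedness grades in section 18.7 overlap because the two ends rest on timing alone, and section 18.2 reuses the labels without defining them or setting a clear cut-off for an adverse device effect

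*Combined protocol and SAP*

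**What the plan says.** Section 18.7 introduces a five-grade relatedness scale with the words "When reporting the SAE, the relationship to the test material shall be described whether the event is considered". *Not related* means that "the event has no temporal relationship with the use of the test material or the procedures". *Definitely related/Causal relationship* means that "the event has a temporal relationship with the test material use/application or procedures". Neither definition mentions mechanism or alternative cause. The three grades between them are worded differently. *Unlikely related*, for instance, covers the case where "the event can be reasonably explained by another cause". There is also a default: "Cases where relatedness cannot be assessed, or no information has been obtained should also be classified as possible".

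Section 18.2 defines the device effect: "An adverse event, which is related to the use of the investigational medical device, is an adverse device effect". It then says that such an event "should be marked as unlikely related, possible related, probably related or with causal relationship on the adverse event form". These labels nearly match those of section 18.7, but section 18.2 does not define them and does not refer to section 18.7.

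Section 2 states what the data are for: they will be compared with data on similar devices "to ensure the performance and safety profile for Biatain Fiber Ag is similar to other antimicrobial gelling fibers". Table 4 in section 18.2 lists six anticipated ADEs with likely incidence rates of 1% to 10%.

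**The concern.** A relatedness scale should place each event in one grade. Here the two end grades depend on timing and the middle three on causal plausibility, so one event can satisfy the wording of two grades at once. Timing also discriminates poorly in this trial, because section 5.1 has subjects using the dressing throughout the two-week test period.

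The trial has one arm and no concurrent control, so relatedness grading is the main way the plan separates device effects from background events. If investigators at up to 10 sites (section 1.2) apply the wording differently, the overall ADE and serious ADE counts depend partly on who graded them. That weakens the comparison with similar devices that section 2 describes.

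**Working it through.** No figure in the plan is at issue, so the check sets the texts side by side.

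**Step 1. The five grades in section 18.7.**

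| Grade | Timing criterion | Causal or alternative-cause criterion |
|---|---|---|
| Not related | must be absent | none |
| Unlikely | none | relationship seems irrelevant and/or another cause explains the event |
| Possibly | none | weak link, other causes possible; also the default |
| Probably | none | link seems relevant and/or no other reasonable cause |
| Definitely/causal | must be present | none |

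**Step 2. A serious event during wear that another cause explains.** Take temporal relationship to mean that the event coincides with use.
- *Not related* fails, because the event coincides with use.
- *Definitely related* is met in full, because timing is its only condition.
- *Unlikely related* is also met, because another cause explains the event.

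The event fits two grades near opposite ends of the scale, and no rule says which prevails. The exceptions are events before first application or after use has ended, away from any study procedure.

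**Step 3. Carry the scale into section 18.2.** The four grades other than *Not related* correspond to the four that section 18.2 lists for an ADE. If section 18.7 supplies their meaning, an event during wear has no grade outside the ADE list. What can keep it out is section 18.2's opening condition that the event be related to device use. The only stated test for *Not related*, however, is the timing test. Including *unlikely related* as an ADE grade also sits awkwardly with that opening condition.

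**Step 4. What the grade changes (sections 18.4.1, 18.5 and 18.7).**

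| | Serious event | Non-serious event |
|---|---|---|
| Count affected | serious ADE | ADE |
| 24-hour report to sponsor | required either way | required if an ADE |
| Follow-up if ongoing at termination | listed either way | listed if an ADE, otherwise none |

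For serious events, where the definitions expressly apply, the grade changes the serious ADE count but neither of these two duties. For non-serious events the grade decides both, and there the plan gives no definitions of its own.

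**Step 5. Table 4.** Its rows are skin irritation/inflammation 10%, allergic skin reaction 1%, maceration 10%, pain 10%, hyper-granulation 5% and blistering 2%. The burn itself could produce pain, blistering and irritation, so those rows are exposed to misattribution. A coincidental headache adds to the overall ADE count but to none of the dressing-specific rows.

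**Step 6. Can the inflation be sized?** Not from the documents: they give no background rate of unrelated events and no share that would be misattributed. The only arithmetic Table 4 allows is the combined rate of any anticipated ADE, assuming that the rates are per subject and the rows independent: 1 − (0.90³ × 0.99 × 0.95 × 0.98) = 1 − 0.672 = 0.328, about 33%. If, in addition, an assumed 10%, 20% or 40% of subjects had an independent unrelated event and every one was misattributed, the share with any ADE would be 1 − 0.672 × 0.90, 0.80 or 0.60, about 40%, 46% or 60%. These are ceilings under stacked assumptions, not estimates.

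**The case against.** The case on the other side has four parts.

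- **Scope.** The definitions are introduced for serious events, and most events expected here would be non-serious. No text extends the definitions to them, and the adverse event form, which may carry its own, is not among the documents. This stands as a limit on the literal argument. It also means that, in these documents, non-serious events have labels without definitions, although section 18.7 has the investigator assess serious and non-serious events alike.
- **The opening condition in section 18.2.** An investigator can screen out unrelated events before choosing an ADE grade. This stands in part: it makes sensible grading possible but supplies no test of relatedness and leaves *unlikely related* on the list.
- **Ordinary reading.** The top grade is labelled causal, the scale is ordered, and *unlikely* expressly takes events with another explanation. Many investigators would read temporal relationship as a plausible sequence, not mere coincidence. That is fair, but others may not, and the text does not settle it.
- **Limited harm.** Section 10.5 pre-plans no test beyond the primary analysis, section 10.2 lists all data, and the error runs mostly towards over-reporting. All of this stands and bounds the importance of the point.

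A reader might infer that almost every adverse event becomes a device effect, with a day-3 headache as the example. The documents do not support that: it needs the serious-event scale to be applied to all events and section 18.2's opening condition to be set aside. A reader might also infer that comparison with Table 4 becomes impossible. It does not, because Table 4 is organised by event type. Nor can the inflation be sized by adding a background rate to a single 10% row, since that treats one of six rows as the rate of any ADE. Finally, two-month follow-up would not attach to every coincidental event, because section 18.5 limits it to events ongoing at termination.

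**Conclusion.** The point holds as a defect of definition. The end grades in section 18.7 rest on timing alone and overlap with the middle grades, section 18.2 borrows the labels without defining them, and no other section resolves either matter. For serious events this follows directly from the text, on the literal reading of temporal relationship. For non-serious events it rests on the further assumption that sites carry the section 18.7 scale over to section 18.2, which the near-identical labels invite but no sentence requires.

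What is affected is the overall ADE and serious ADE counts, the 24-hour reporting and post-termination follow-up of non-serious events, and the Table 4 rows that the burn itself could produce. The direction is mainly inflation, with inconsistency between sites. The amount is unknown. The primary endpoint, its test and the sample size are unaffected. The change should be made, but it does not threaten the trial's main conclusion.

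**What to change.** Reconcile sections 18.2 and 18.7 and align the adverse event form with them:

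- Make the five grades mutually exclusive.
- Define *Definitely related* by a temporal relationship together with the absence of a reasonable alternative cause.
- Allow *Not related* for an event during wear that another cause fully explains.
- State that the scale applies to all adverse events, serious or not.
- State in section 18.2 which grades count as an ADE. A workable cut-off is possible, probable and causal, with *unlikely related* tabulated separately.

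The cost is wording in two sections, an updated form and retraining of sites. No new data are needed. If grading has already begun, events graded under the current wording would need to be regraded or reported separately.

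### Section 18.7 defines adverse-event intensity by the action taken, so the recorded grade partly reflects treatment practice rather than how intense the event was

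*Combined protocol and SAP*

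**What the plan says.** Section 18.1 sets the requirement for all adverse events: "The adverse event shall be marked with the intensity mild, moderate, or severe". It does not say what the three words mean.

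The definitions come in section 18.7, in a passage that begins with how to report an SAE:

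- For the lowest grade, Mild, the test is that "the intensity of the event is mild with no further action or intervention".
- For the middle grade, Moderate, the test is that "the intensity of the event will lead to an action or intervention to solve the event".
- For the highest grade, Severe, the test is that "the intensity of the event will lead to follow up on the action or intervention". The reason the section gives for this is put as follows: "as the effect of the action or intervention may not decrease the symptoms".

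No other definition of intensity appears in the document. Seriousness is a separate matter: section 18.4 opens with "A serious adverse event is an adverse event that" and lists outcome-based criteria that do not refer to the intensity grade. Table 4 in section 18.2 lists anticipated device effects and their incidence by type, without grades.

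**The concern.** An intensity grade should say how bad the event was for the subject. Whether it was treated, and whether treatment worked, are different facts that belong in other fields. Section 18.7 merges them. No level mentions degree of discomfort or limitation of activity. The word mild appears inside the definition of Mild, which makes that part circular and leaves the no-action condition to do the work.

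Adverse events are one of the two safety assessments named in section 5.2, and intensity is a required attribute of each. The study is open and single-arm and uses up to 10 sites (section 1.2). If the grade depends on whether something was done, sites that intervene readily for minor complaints will record more Moderate events than sites that watch and wait, even for the same reactions. A reader of the safety listing could not tell the two explanations apart.

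**Working it through.** No arithmetic decides this point, and the plan states no figure to reproduce. The check is to apply the three definitions, as worded, to four kinds of event.

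| Event | Mild? | Moderate? | Severe? | Result |
|---|---|---|---|---|
| Slight, nothing further done | Yes | No action | No action | Mild |
| Slight, treated once, settles | Excluded: there was an action | Yes | No follow-up of the action called for | Moderate |
| Intense, no action needed | Excluded: not mild | Excluded: no action | Excluded: no action to follow up | No level fits |
| Grave, treated, responds | Excluded | Fits if no follow-up of the action is expected | Fits if follow-up is expected when the event is graded | Not determined by the text |

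**Row 2** follows directly from the wording. Headache is one of section 18.1's own examples of an adverse event. A slight headache given a single treatment fails the no-action condition and becomes Moderate. An untreated headache of the same intensity is Mild.

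**Row 3** shows that the scale is incomplete. The two upper grades both presuppose an action, and the lowest presupposes that the event is mild.

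**Row 4** is open. The Severe definition looks forward, to follow-up that the event will lead to and to an action that may not help. It does not ask whether treatment in fact succeeded.

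**Scope.** Section 18.1 asks for a grade on all adverse events, while the sentence that introduces the definitions speaks of reporting an SAE. Non-serious events are therefore graded either on a scale not expressly written for them or on each investigator's own understanding.

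**Size.** The Table 4 rates sum to 10 + 1 + 10 + 10 + 5 + 2 = 38 events per 100 subjects. In 50 subjects that is 0.38 × 50 = 19 anticipated device effects, if each subject has at most one of each type. To say how many would be misgraded one also needs the share that receive some further action and the share of those that are slight. The documents give neither. With each share free to lie between 0 and 1, the answer for these events lies anywhere between 0 and 19, which is not an estimate. Adverse events unrelated to the device would come on top, and no rate is given for them.

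**The case against.** The strongest reply is that little depends on the intensity grade. Seriousness under section 18.4 is independent of it. So are the 24-hour reporting rule in 18.7, the sponsor's deadlines in 18.8 and the follow-up arrangements in 18.5. Section 10 promises listings of all collected data and general summaries, but it names no table by intensity and no safety hypothesis. With 50 subjects each event can be read individually. All of this stands, and it is why the point is minor.

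Second, the wording does name intensity, and Mild excludes only further action. Routine wound care, including the barrier cream that section 7.1 lists as an additional product, need not raise the grade. That also stands. It narrows the problem to treatment given because of the event but does not remove it.

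A reader might infer four stronger things that the documents do not support:

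- *A grave reaction that responds to treatment must be graded Moderate.* The forward-looking wording lets an investigator grade it Severe at onset.
- *The scale duplicates the seriousness criteria.* Section 18.4 covers hospital admission and interventions against life-threatening or permanent harm. It does not capture ordinary treatment of non-serious events, which the intensity scale does pick out.
- *The comparison with similar devices planned in section 2 is spoiled.* The safety figures the plan shows for other silver products, in Table 4, are incidences by type. Nothing in the documents shows how other studies graded intensity.
- *Conditions needing antibiotics (section 5.6) are misgraded.* By rule none can be Mild, but at least Moderate is not evidently wrong for them.

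Finally, the adverse-event form is not part of the documents, so separate fields for action and outcome cannot be said to be missing.

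**Conclusion.** The concern holds in limited form. The only definitions of a required safety variable sort events by action and expected response. They force slight treated events out of Mild, leave intense untreated events without a grade, and are introduced for serious events only. Recorded intensity is therefore partly a record of treatment practice.

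The consequence is confined to the intensity grade and its consistency between sites. Counts of adverse events, their seriousness, causality and expedited reporting, and the primary healing endpoint do not change. The number of events affected cannot be estimated from the documents.

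The conclusion rests on reading 18.7 literally and on no further grading guidance being in use. If the form or the site training material already defines intensity by symptoms, the practical effect is smaller, but the CIP text should then be brought into line with it.

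**What to change.** In section 18.7, replace the three definitions with ones based on the degree of symptoms or discomfort and on interference with usual activity attributable to the event. For example:

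- *Mild:* slight symptoms or discomfort, with no interference with usual activity from the event.
- *Moderate:* clear discomfort, or some interference with usual activity.
- *Severe:* marked discomfort, or usual activity prevented.

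Two conditions matter here. Interference must be judged over and above the limits set by the burn itself, because a burn can restrict activity before any adverse event occurs. The symptom criterion must also be able to stand alone, because a local skin reaction may be unpleasant without limiting activity.

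State in 18.7 that the scale applies to all adverse events, serious or not, and refer to it from 18.1. Keep action taken and outcome as separate items on the adverse-event form, adding them if they are not already there, so that the information now mixed into the grade is not lost.

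The cost is revised CIP and form wording and updated training text, with no extra visits, subjects or measurements. The downside is that some events will move between grades, possibly with more counted as severe.
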